7.1.4 Causality

The investigator must assess the causality of all reportable serious adverse events in relation to the trial intervention or procedures using the definitions in Table 4.

Relationship	Description	
Unrelated	There is no evidence of any causal relationship	
Unlikely to be related	There is little evidence to suggest that there is a causal relationship. There is another reasonable explanation for the event (e.g. the participant's clinical condition or other concomitant treatment)	
Possibly related	There is some evidence to suggest a causal relationship. However, the influence of other factors may have contributed to the event (e.g., the participant's clinical condition or other concomitant treatment)	
Probably related	There is evidence to suggest a causal relationship and the influence of other factors is unlikely	
Definitely related	There is clear evidence to suggest a causal relationship and other possible contributing factors can be ruled out	

Table 3: Causality definitions

7.1.5 Severity of adverse events

The severity of all reportable SAEs should be graded using the following table:

Table 4: AE severity grading

Intensity	Definition
Mild	Participant is aware of signs and symptoms, but they are easily tolerated
Moderate	Signs / symptoms cause sufficient discomfort to interfere with usual activities
Severe	Participant is incapable of working or performing usual activities

NB. The term "severe" is often used to describe the intensity (severity) of a specific event. This is not the same as 'serious', which is based on patient/event outcome or action criteria (see definition in Table 2).

7.1.6 Expectedness

If there is at least a possible relatedness to the trial intervention or procedures, the Chief Investigator must assess the expectedness of the event. An unexpected event is one that is not reported in the protocol, or one that is more frequently reported or more severe than previously reported.

The following are 'expected' maternal events:

- Hypoglycaemia (including severe hypoglycaemia)
- Hyperglycaemia, ketosis, HHS, DKA

The following are 'expected' events in the infant:

- Birth injury
- Congenital or chromosomal anomalies
- Admission to neonatal unit
- Neonatal hypoglycaemia (including hypoglycaemic seizures)
- Hyperbilirubinemia
- Respiratory distress
- Shoulder dystocia

7.3 Notifications

7.3.1 Notifications by the Investigator to NCTU

If the event meets the criteria for 'serious' (Table 2) then a SAE form must be completed and forwarded to NCTU. This should be **immediately, and in no circumstances later than 3 calendar days** after the Investigator becomes aware of the event.

Investigators should notify NCTU of related SAEs occurring from consent until maternal post-partum hospital discharge. If the participant discontinues with the intervention, SAEs considered related to the intervention should still be reported.

The SAE form must be signed off by the Principal Investigator (PI) or other investigator with delegated responsibility, with attention paid to the severity and causality of the event. In the absence of the PI (or delegate), the SAE form should be completed and signed by a member of the site trial team and emailed as appropriate within the timeline. The PI/delegate should check the SAE form at the earliest opportunity, make any changes necessary, sign and then email to NCTU. Detailed written reports should be completed as appropriate. Systems will be in place at the site to enable the PI to check the form for clinical accuracy as soon as possible.

The minimum criteria required for reporting an SAE are the trial number and date of birth, name of reporting person and sufficient information on the event to confirm seriousness. Any further information regarding the event that is unavailable at the time of the first report should be sent as soon as it becomes available.

The SAE form must be scanned and sent by email to the NCTU central safety email account ([contact]).

Participants must be followed up until clinical recovery is complete / laboratory results have returned to normal or baseline values, or until the event has stabilised. Follow-up should continue after completion of protocol intervention and/or trial follow-up if necessary. Follow-up SAE forms (clearly marked as follow-up) should be completed and emailed to NCTU as further information becomes available. Additional information and/or copies of test results etc. may be provided separately. The participant must be identified by trial number, date of birth and initials only. The participant's name should not be used on any correspondence and should be blacked out and replaced with trial identifiers on any test results.

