6.10.4.5 Safety evaluation

Serious Adverse Events will be tabulated by treatment group and statistical tests performed as appropriate.

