6.11.3 Data monitoring for harm

Adverse events will be collected as per section 7 and analysed according to the Statistical Analysis Plan. Serious Adverse Events (SAEs) by treatment group will be reviewed by the DMC as described in their terms of reference.

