7.1 Investigator responsibilities relating to safety reporting

Participants will be reviewed for adverse events at all study visits. Non-serious AEs do *not* need to be reported to NCTU, however should be recorded per local policies. SAEs and Adverse Events of Special Interest (AESI), should be reported to NCTU in line with the below:

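### Section 7.3.1 gives two conflicting rules for notifying SAEs; the narrower one filters events by unblinded relatedness and stops at maternal discharge, leaving the by-arm SAE comparison open to bias and incomplete

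*Protocol*

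**What the plan says.** Protocol Section 7.3.1 opens with an unrestricted rule: "If the event meets the criteria for 'serious' (Table 2) then a SAE form must be completed and forwarded to NCTU". It sets no condition on causality and no end date. The next paragraph says: "Investigators should notify NCTU of related SAEs occurring from consent until maternal post-partum hospital discharge". It then adds: "If the participant discontinues with the intervention, SAEs considered related to the intervention should still be reported".

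Section 7.1 states the general duty without a causality limit: "SAEs and Adverse Events of Special Interest (AESI), should be reported to NCTU in line with the below". Section 7.1.4 has the investigator grade causality for all reportable SAEs, on a scale (Table 3) whose first category is *unrelated*.

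The data have two planned uses. Section 6.10.4.5: "Serious Adverse Events will be tabulated by treatment group and statistical tests performed as appropriate". Section 6.11.3: "Serious Adverse Events (SAEs) by treatment group will be reviewed by the DMC". Section 6.8.2 states that the trial is unblinded for participants and care teams.

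Section 7.1.2 lists stillbirth and neonatal death among the SAEs. Section 6.10.4.3 counts a neonatal death up to 28 days of life.

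**The concern.** A by-arm SAE comparison is interpretable only if an event has the same chance of being recorded in either arm. Under the second paragraph of 7.3.1, an event is notified only if site staff, who know the allocation, judge it related to the intervention or to trial procedures. That judgement may differ by arm, because only one arm wears the real-time sensor throughout. The tables, tests and DMC review would then reflect attribution as well as incidence.

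Central review does not repair this. Section 7.3.2 has a Co-Chief Investigator review the reports received, so an event that was never notified is not seen there.

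The window is a second problem. It closes when the mother is discharged, whereas a listed SAE, neonatal death, is defined to day 28. A baby who dies in the neonatal unit after the mother has gone home falls outside the notification sentence.

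**Working it through.** The protocol gives no SAE rate, no proportion judged related and no power figure for SAEs, so there is no stated figure to reproduce. The check is mainly textual.

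**1. Which events are notified?**

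| Place | Rule on causality | End of window |
|---|---|---|
| 7.1 | none stated | none stated |
| 7.1.4, Table 3 | graded after the fact; *unrelated* is a valid grade | not applicable |
| 7.3.1, first paragraph | none | none stated |
| 7.3.1, second paragraph | related only | maternal post-partum discharge |

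An unrelated, non-exempt SAE must be notified under the third row and need not be under the fourth. A scale that includes *unrelated* fits only the unrestricted rule. The sentence on women who stop the intervention can be read either way: as repeating the filter, or as implying a broader duty before stopping.

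**2. Which listed SAEs depend on the SAE form?** Taking the events in 7.1.2 in turn:

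- Severe hypoglycaemia and HHS/DKA are also adverse events of special interest, recorded on their own eCRF without a relatedness filter (7.1.1). Section 6.10.4.3 compares them by arm.
- Stillbirth and neonatal death are also part of the primary neonatal outcome (6.5.1) and the secondary outcomes (6.5.2).
- Maternal death and severe skin reaction have no equivalent unfiltered route, nor do non-exempt SAEs outside these lists.

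**3. The infant window.** Infant data run to neonatal discharge, or to 28 days if admission is prolonged (6.3.1.4, 6.6.1.10). A death in the unit after maternal discharge should therefore reach the outcome data but not the SAE record. A death at home after the infant's discharge and before day 28 is not clearly covered by either route.

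**4. Illustration only.** Assume the same true SAE risk in both arms and 211 women per arm (Section 2.3). Expected notified events per arm = 211 × true risk × probability of being judged related. Rejection is the exact probability that a two-sided 5% Fisher test rejects. Risks and probabilities are assumptions. At a true risk of 10%:

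| Judged related, CGM / control | Expected notified, CGM / control | Fisher rejects |
|---|---|---|
| all notified | 21.1 / 21.1 | 3.5% |
| 10% / 10% | 2.1 / 2.1 | 0.6% |
| 10% / 2% | 2.1 / 0.4 | 1.4% |
| 25% / 5% | 5.3 / 1.1 | 21.8% |
| 50% / 10% | 10.6 / 2.1 | 59.5% |

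For example, 211 × 0.10 × 0.25 = 5.3 and 211 × 0.10 × 0.05 = 1.1. With true risks from 5% to 20% and the same pairs, false rejection runs from 0.1% to 93.5%. A five-fold difference in attribution gives a five-fold spurious ratio. Equal attribution at 10% gives no bias between arms but loses 90% of events (2.1 instead of 21.1 per arm). With no filter, the test rejects 3.0%, 3.5% and 3.8% of the time at true risks of 5%, 10% and 20%, so it keeps its level.

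**The case against.** The best case for the plan is that most of the text points to all serious events. The first paragraph of 7.3.1, Section 7.1 and Table 3 all do. So do the minimum criteria for a report, which ask for seriousness and not causality. Sections 7.1.6 and 7.3.2 use relatedness as a later filter, which would be largely redundant if only related events arrived. On this view the second paragraph is a drafting slip.

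This stands in part. A reader might infer that notification simply is limited to related SAEs; the documents do not support that, because the limit is one of two conflicting rules. But the slip is not harmless. The second paragraph is the only place in 7.3.1 that states a reporting window, so sites will consult it, and Section 7.1 sends them to the text below it.

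A reader might also infer that control women have almost nothing to which an event could be related. That is not so. They wear masked sensors for 14 days at each of four time points (6.4.2.1, 6.6.1.7), 4 × 14 = 56 days, besides the baseline sensor, and relatedness covers trial procedures. Their exposure is lower, not negligible.

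Nor do the documents support the inference that the DMC would miss most serious events. Several listed events are captured by other routes, and the committee's remit lies in terms of reference that are not shown.

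Finally, the analysis set for 6.10.4.5 may be settled in a SAP that is not at hand. That is fair, but a SAP cannot restore events that were never notified.

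**Conclusion.** The point holds as an internal contradiction with a consequence. If sites follow the second paragraph of 7.3.1, the by-arm SAE tables, tests and DMC review rest on events selected by an unblinded judgement that may differ by arm. The comparison is then open to bias and incomplete. Sites following different paragraphs would also report different events.

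It would go too far to say that the comparison *is* biased, or biased against CGM. Size and direction depend on differences in attribution that the documents do not quantify; the illustration spans almost the whole range. It would also go too far to say that late neonatal deaths are lost to the trial: a death during the infant's admission, up to day 28, should still be captured as outcome data. What is misaligned is the SAE record.

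The main exposure is maternal death, severe skin reaction, other non-exempt SAEs, and the SAE record of neonatal deaths after maternal discharge.

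**What to change.** Reconcile 7.3.1 with 7.1, 7.1.2 and 7.1.4:

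- Remove the word *related* from the notification sentence, so that all non-exempt SAEs in both arms are notified whatever the causality. Bring the sentence on women who stop the intervention into line.
- Keep relatedness as the criterion for onward reporting in 7.3.2.
- State that the tabulation and tests in 6.10.4.5 use all-causality SAEs.
- Align the SAE window for neonatal death with the 28-day definition in 6.10.4.3.

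This is a short wording change. The cost is a modest increase in SAE forms, which the exemptions in 7.1.3 keep low because they already remove the common obstetric and infant events.

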7.3.2 Reporting procedures for SAEs

A Co-Chief Investigator (or a medically qualified delegate) will review all SAE reports received. In the event of disagreement between the causality assessment given by the local investigator and the Co-CI (or delegate), both opinions and any justifications will be provided in subsequent reports.

The delegated staff at NCTU will cross reference the SAE against expected events specified in the protocol to determine onward reporting requirements. This expectedness assessment will be reviewed and signed off by a Co-Cl.

SAEs considered to be related to the CGM system will be reported to the manufacturer in line with the contract.

SAEs should be reported to the main REC within 15 days of the NCTU becoming aware if, in the opinion of the CI, the event was both:

- Related to the study i.e., resulted from the administration of the CGM or trial procedures
- Unexpected i.e., not listed in the protocol as an expected occurrence.

NCTU will keep investigators informed of any safety issues that arise during the course of the trial.

7.3.3 Other safety monitoring

7.3.3.1 Suicidal ideation or a risk of self-harm on a self-reported PHQ-9 Questionnaire

The eCRF will be designed to immediately flag the entry of data that indicates suicidal ideation or a risk of self-harm (defined as any participant scoring 1 ('several days') or above on item 9 of PHQ-9 ('How often in the past two weeks have you had thoughts that you would be better off dead or of hurting yourself in some way?).

In the event of the above, an email will be generated by the eCRF and sent to the PI and local site team.

The recruiting site should follow its standard local mental health procedures to ensure the safety and wellbeing of the participant is maintained.

8 Ethics and dissemination

8.1 Research Ethics and Health Research Authority approval

Before initiation of the trial at any clinical site, the protocol, all informed consent forms, and trialspecific material to be given to the prospective participant will be submitted to the relevant REC and to HRA for approval. Any subsequent amendments to these documents will be submitted for further approval.

The rights of the participant to refuse to participate in the trial without giving a reason must be respected. After the participant has entered the trial, the clinician remains free to give alternative treatment to that specified in the protocol, at any stage, if s/he feels it to be in the best interest of the participant. The reasons for doing so must be recorded. After randomisation, the participant must remain within the trial for the purpose of follow up and data analysis according to the treatment option to which they have been allocated. However, the participant remains free to change their mind at any time about the protocol treatment and follow-up without giving a reason and without prejudicing their further treatment.

8.2 Other approvals

Documentation will need to be submitted to the R&D Department at each NHS Trust in order to gain confirmation of capacity and capability (for English sites) or local R&D approval (for non-English sites) prior to the study being initiated at that Trust.

A copy of the local capacity and capability / R&D approval must be forwarded to the NCTU, before participants are randomised to the trial.

The protocol has received formal approval and methodological, statistical, clinical and operational input from the NCTU Protocol Review Committee.

8.4 Amendments

Amendments to the protocol and other documents (e.g., changes to eligibility criteria, outcomes, sample size calculations, analyses) will be agreed by the CIs and / or TMG for more notable changes. Such amendments will be forwarded to the Sponsor for confirmation as to whether it is either substantial or non-substantial and will then be submitted to the Health Research Authority and Ethics Committee for categorisation and approval. Once the amendment has been categorised it will be sent to relevant sites for consideration in accordance with standard HRA processes and timescales. Amendments must not be implemented until HRA approval is received and sites have either confirmed acceptance or, no objection has been received within the defined timescale. Notification will be sent by NCTU to trial personnel to confirm when an amendment can be implemented.

8.5 Consent or assent

Patients will be provided with the patient information (paper or digital Patient Information Sheet (PIS)) and given time to read it fully. Following a discussion with a medical qualified investigator or suitable trained and authorised research team member, any questions will be satisfactorily answered and if the participant is willing to participate, written informed consent will be obtained. During the consent process, it will be made completely and unambiguously clear that the participant is free to refuse to participate in all or any aspect of the trial, at any time and for any reason, without incurring any penalty or affecting their treatment.

Consent will be re-sought if new information becomes available that affects the participant's consent in any way. This will be documented in a revision to the patient information sheet and the participant will be asked to sign an updated consent form. These will be approved by the ethics committee prior to their use.

Consent will be taken (optional) for potential future metabolic and National Pregnancy in Diabetes (NPID) linkage studies.

A copy of the approved consent form is available from the NCTU trial team.

8.5.1 Consent or assent in ancillary studies

Consent will be taken for potential metabolic and National Pregnancy in Diabetes (NPID) data linkage studies.

8.6 Confidentiality

Any paper copies of personal trial data will be kept at the participating site in a secure location with restricted access. This information will be securely destroyed 10 years after the end of the trial.

Confidentiality of patient's personal data is ensured by not collecting patient names on CRFs and limiting access to personal information held on the database. At trial enrolment, the patient will be issued a participant identification number and this will be the primary identifier for the patient, with secondary identifiers of date of birth and initials.

The patient's consent form will carry their name and signature. These will be kept at the trial site, with a copy uploaded to the study database for monitoring purposes. This copy will be deleted once checks are complete.

8.7 Declaration of interests

The investigators named on the protocol have no financial or other competing interests that impact on their responsibilities towards the scientific value or potential publishing activities associated with the trial.

8.8 Indemnity

The NHS indemnity scheme will apply to the potential liability of the sponsor for harm to participants arising from the management and conduct of the research. UEA holds insurance to cover harm to participants arising from the design of the study.

8.9 Finance

PROTECT is fully funded by an NIHR Health Technology Assessment (HTA) grant ID NIHR150958. Trial CGM devices are supplied free of charge from Abbott Diabetes Care, Inc.

8.10 Archiving

The investigators agree to archive and/or arrange for secure storage of PROTECT trial materials and records for 10 years after the close of the trial unless otherwise advised by the NCTU.

8.11 Access to data

Requests for access to trial data will be considered, and approved in writing where appropriate, after formal application to the TMG/TSC. Considerations for approving access are documented in the TMG/TSC Terms of Reference.

8.12 Ancillary and post-trial care

Devices will be provided to the participants for the duration of the trial. Post-trial care is at the discretion of the woman and her treating clinical team.

8.13 Publication policy

8.13.1 Trial results

Data will be published in internationally peer-reviewed scientific journals; members of the investigator group and clinical collaborators will be included as co-authors as appropriate.

The results of the trial will be disseminated regardless of the direction of effect.

8.13.2 Authorship

Authorship will be determined by a publication policy which will be agreed by the TMG.

8.13.3 Reproducible research

The trial will be registered on the ISRCTN website, granting public access to the trial outcomes. In addition, the clinical study protocol will be submitted for publication. Every effort will be made to grant access to the participant-level dataset subject to TSC approval.

9 Outcome definitions

Early onset type 2 diabetes: T2D diagnosed before 39 years of age.

Booking appointment: first antenatal visit following confirmation of pregnancy.

Birth injury: includes spinal cord injury, clavicular fracture, basal skull fracture, depressed skull fracture, long bone fracture (humerus, radius, ulna, femur, tibia or fibula), shoulder dystocia, peripheral nerve / brachial plexus injury, subdural or intracerebral haemorrhage confirmed by computerized tomography (CT) or magnetic resonance imaging (MRI) scan, hypoxic ischaemic encephalopathy.

Neonatal hyperbilirubinemia: Significant jaundice based on bilirubin levels requiring treatment with either phototherapy, or an exchange transfusion, or receiving intravenous gamma globulin or requiring readmission into hospital during the first 7 days of life due to hyperbilirubinemia.

Neonatal hypoglycaemia: A capillary glucose <2.2mmol/L on one or more occasions, within the first 48 hours after delivery starting at least 30 minutes after birth and necessitating treatment either with 40% glucose gel administered to the buccal mucosa and/or with intravenous glucose.

Respiratory distress: Respiratory difficulties requiring supplemental oxygen and/or any positive pressure ventilation, beyond resuscitation period (10 minutes), and /or given surfactant within 72 hours after birth.

Levels of neonatal care based on BAPM 2011 Categories of Care:

- **Transitional care** is provided in some units, where the mother is resident with her baby and providing care with minimal support from a midwife/healthcare professional. E.g., low birthweight babies, babies receiving antibiotics or phototherapy.
- Special Care is for babies who require additional care but do not require either Intensive or High Dependency care. E.g., oxygen by nasal cannula, feeding by nasogastric, jejunal tube or gastrostomy, continuous physiological monitoring (excluding apnoea monitors only), care of a stoma, presence of IV cannula, baby receiving phototherapy, special observation of physiological variables at least 4 hourly
- High Dependency Care is for babies who require highly skilled staff but where the ratio of nurse to patient is less than intensive care. E.g., requiring non-invasive respiratory support (e.g., nasal CPAP, SIPAP, BIPAP, HHFNC); parenteral nutrition; continuous infusion of drugs (except prostaglandin &/or insulin); presence of a central venous or long line (PICC); presence of a tracheostomy; presence of a urethral or suprapubic catheter, presence of transanastomotic tube following oesophageal atresia repair, presence of NP airway/nasal stent, observation of seizures / CF monitoring, barrier nursing, ventricular tap.
- Intensive Care is for the most unwell babies, typically those delivered preterm and/or needing respiratory support, or other high-level care.

Preterm birth: Preterm birth (<37 weeks and early preterm <34 weeks).

Shoulder dystocia: Defined as a vaginal cephalic delivery that requires additional obstetric manoeuvres to deliver the fetus after the head has delivered and gentle traction has failed (https://www.rcog.org.uk/en/guidelines-research-services/guidelines/gtg42/).

Hyperglycaemia: high blood sugar (glucose level).

Hyperosmolar hyperglycaemic state: hyperglycaemia \geq 30 mmol/L, hyperosmolality (effective serum osmolality usually \geq 320 mOsm/kg), and volume depletion in the absence of significant ketoacidosis.

Hypoglycaemia: low blood sugar (glucose level).

Severe hypoglycaemia: An event requiring assistance of another person actively to administer carbohydrate, glucagon, or other resuscitative actions. Severe hypoglycaemia will be categorised as treated at home with rescue carbohydrates and/or glucagon, requiring ambulance or paramedic call out, requiring hospital admission.

Diabetic ketoacidosis (DKA): requiring hospital admission and treated with intravenous insulin infusion (as defined by the Joint British Diabetes Societies)

Maternal hypertensive disorders: includes gestational hypertension, worsening of pre-existing hypertension, and/or preeclampsia defined as:

- Gestational hypertension: Systolic blood pressure ≥140 mmHg and/or diastolic blood pressure ≥90 mmHg on at least two occasions four hours apart, developing after 20 weeks of gestation in previously normotensive women.
- Pre-eclampsia: Hypertension accompanied by proteinuria ≥300 mg in 24 hours, or two readings of at least ++ on dipstick analysis of urine or documentation of pre-eclampsia in the delivery or antenatal records.
